University of Kansas Medical Center RESEARCH PROTOCOL INVOLVING HUMAN SUBJECTS

Version date: 4/21/22

Principal Investigator: [name]

Study Title: Impact of statin therapy on muscle mitochondrial function and aerobic capacity

Co- Investigator(s): [name], [name], [name]

I. Purpose, Background and Rationale

A. Abstract

More than 40 million Americans are currently take statins for the treatment or prevention of hyperlipidemia and cardiovascular disease (CVD). Based on the new usage guidelines from the American College of Cardiology and the American Heart Association (ACC/AHA) (2), that number is expected to increase to over 60 million (3), reflecting the growing sentiment for more wide-spread use of statins, even in otherwise asymptomatic patients. Although generally well-tolerated, statin therapy is not without risks. The most common reported side effects include mild to moderate muscle weakness, fatigue and/or pain, the incidence of which increase as a function of both dose and duration of statin use (4, 5). Stating also increase the risk of developing more serious metabolic conditions, including insulin resistance and type 2 diabetes (6-9). The underlying mechanism(s) for these complications is unknown. In recent years however, evidence has been mounting from both cell culture and animal models that statins interfere with mitochondrial function in muscle (10-12). In the present application, we provide data from both ex vivo and in vivo preliminary studies in humans suggesting that statins induce progressive and quite striking reductions in skeletal muscle mitochondrial respiratory function. The overall aim of the study is to determine the impact of low and high dose statin therapy on skeletal muscle mitochondrial function, insulin sensitivity, and cardiorespiratory fitness. Our hypothesis is that statin therapy produces a decline in mitochondrial respiratory function in skeletal muscle that is both dose and duration dependent, compromising metabolic and cardiorespiratory function.

B. Background and Significance

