concentrations of atorvastatin. Statin exposure did not affect complex I or II activity (not shown), but did inhibit complex III at mM concentrations (Fig. 5A & 5B), similar to a recent report (12). Strikingly, atorvastatin inhibited complex IV at concentrations as low as 10 nM (Fig. 5C & 5D), which equated to ~7.5 ng/g cell protein, similar to the concentration range (~5-18 ng/g protein) of atorvastatin detected by mass spec in muscle from participants undergoing the statin therapy. Sensitivity to statins has not previously been reported for complex IV, providing a potential mechanism for the compromised respiratory capacity observed in vivo (Fig. 4).

These findings are preliminary evidence that skeletal muscle mitochondrial respiratory capacity and function declines rapidly with high dose atorvastatin therapy. These findings are consistent with several factors that are likely to be at play simultaneously that affect the net effect of statins on mitochondrial and whole muscle function in vivo, emphasizing the need for a long-duration, dose-response study in humans. These factors include:

- 1. Intramyofiber statin concentration relative to the density of mitochondria in the myofiber over which the statin is distributed. Factors such as dosage, pharmacokinetics and half-life will determine the concentration and time course over which the statin is present in myofibers (43, 47). Factors determining mitochondrial density in skeletal muscle, which varies considerably among individuals, include genetics, percent fiber type distribution (i.e., type I, IIa and IIx/IIb), age, VO₂peak, and activity level (48). The acute impact of a given dose of statin on mitochondrial respiratory function therefore is most likely transient, driven by the intramuscular statin concentration relative to the mitochondrial density and the turnover rate of the statin.
- 2. Quality of the mitochondria at the time therapy is initiated. Patients with subclinical mitochondrial dysfunction may be predisposed to developing myopathic symptoms, or statin treatment may unmask or induce nascent mitochondrial dysfunction (49). Consistent with this notion, aging, diabetes, obesity, hypothyroidism, renal disease, and frailty are all associated with reduced mitochondrial function in muscle (50, 51), and increased risk of muscle-related adverse reactions to statins (22, 52-54).

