- 3. Mitochondrial respiratory demand relative to intramyofiber statin concentration. Our preliminary data indicate that statin-induced inhibition of respiration increases as a function of ADP-

- stimulated respiratory demand (Fig. 3 & 4). In other words, inhibition is negligible at low rates of respiration, but is clearly present as the demand for respiration increases. This could explain why exercise increases the risk of developing myopathic symptoms (23, 55) and why statins are not well tolerated by athletes (56).
- 4. Declining respiratory reserve capacity over time. Recent reports indicate patients may not present with myopathic symptoms until several years after initiating statin treatment (25). A slowly progressing decline in mitochondrial content as a result of aging and/or inactivity will decrease the density of mitochondria over which the statin is distributed (#1) and increase the relative respiratory demand on the remaining mitochondria (#3). This reduces the available reserve capacity, eventually reaching the point (i.e., threshold) where the decline in function imposed by the statin creates added demand to existing mitochondria that exceeds the reserve capacity and is sufficient to generate myopathic symptoms.

In summary, the goal is to determine if atorvastatin therapy induces a progressive decline in skeletal muscle mitochondrial respiratory function, insulin sensitivity, and cardiorespiratory fitness that is dose and duration dependent.

II. Research Plan and Design

A. Study Objectives: The overall aim of the study is to determine the impact of low and high dose statin therapy on skeletal muscle mitochondrial function, insulin sensitivity, and cardiorespiratory fitness.

a. Primary Objective:

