- C. Sample size, statistical methods, and power calculation: The randomization for study drugs will be carried out by the biostatistician using a computer-based random number generator at a 1:1:1 allocation. Sample size for study is powered on the basis of detecting a difference in mitochondrial respiratory function, the primary outcome measure, between three groups (e.g., placebo, and 20 or 80 mg/d atorvastatin therapy) at 12 months posttreatment. Our pilot study of statin effect on maximal ADP-stimulated O2 consumption rate (JO_2) after 56 days based on 8 participants showed a mean change of 88.5 (pmol/sec/mg) with standard deviation of 59.9 (pmol/sec/mg), which can be standardized into a very large pre-post effect size of -1.48 (Cohen's d). All of these 8 participants experienced a decrease of 11.13% to 66.94% in 56 days, suggesting the decreasing trends are very consistent among participants. The overall decreasing trend of maximal ADP-stimulated O2 consumption rate across all time points also suggests that the decreasing trend will continue beyond 56 days. For the other outcomes variables, insulin-sensitivity and in-vivo O2 recovery kinetics (NIRS), only measurements at baseline and day 56 are available and the observed changes are -0.65 (1.20) (mU/L)⁻¹ min⁻¹ and 19.07 (21.80) mVO₂, which can be standardized into effect sizes of -0.54, and 0.87, respectively. In a much longer study period of 12 month, the within group changes for these variables are expected to be greater. Expecting no change or a small change in the placebo as well as the low-dose group, our primary analyses are two subgroup comparisons: high-dose vs. low-dose and high-dose vs. placebo and the two expected between-group effect sizes (high-dose vs. low-dose and highdose vs. placebo) are large (close to the within-group effect sizes in the pilot data). With 27 participants in each group, a two-sided two sample t-test has 80% power of detecting an effect size of 0.87 (Cohen's d) at 0.025 level to maintain the overall type I error rate at 0.05 level for the two group comparisons. We will recruit 30 participants for each group to allow

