- A. Statistical and Data Analysis: This project is a two-factor study. One factor is treatment group (between participants) and a second factor is time of data collection (0, 1, 6, and 12 months) (within subject). The data analysis will be carried out for the primary outcome variable of mitochondrial respiration in addition to other outcome variables (VO₂peak and insulin sensitivity, etc.). For each measure, its baseline measure and age will be added as covariates to adjust for the individual difference at baseline. Two-way interaction between treatment and time will be added in the model for testing if the outcome changes differently between groups over time. Additional variables, such as demographics, BMI, physical activity, etc. may also be included as covariates. If the test of trend difference is significant, then the comparison at each time point will also be considered to identify when the difference between groups reaches the maximum. Least Square Means will be used for the aforementioned comparisons. The statistical analysis will be performed with mixed procedure in STATA 13.1 (StataCorp LP, College Station, TX). Mixed model does not require complete data for a longitudinal study. Residual analyses will be conducted and efforts to address those will be made, including appropriate transformations.

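### The treatment-by-time interaction is the only stated test over time and a precondition for time-point comparisons: depending on how month 0 is handled, it either cannot show progression or can block the powered month-12 comparison

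*Combined protocol and SAP*

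**What the plan says.** The hypothesis in the Abstract (I.A) is that "statin therapy produces a decline in mitochondrial respiratory function in skeletal muscle that is both dose and duration dependent". The summary closing I.C says that "the goal is to determine if atorvastatin therapy induces a progressive decline in skeletal muscle mitochondrial respiratory function", and V.B expects a decline that depends on both dose and time.

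Section V.A describes the analysis. On time, it says that "a second factor is time of data collection (0, 1, 6, and 12 months) (within subject", so month 0 is listed as a level. It then says: "For each measure, its baseline measure and age will be added as covariates to adjust for the individual difference at baseline", which makes the month-0 value a predictor as well. The one test given is this: "Two-way interaction between treatment and time will be added in the model for testing if the outcome changes differently between groups over time". The next step is conditional: "If the test of trend difference is significant, then the comparison at each time point will also be considered to identify when" the gap between groups is widest.

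Section II.C sizes the trial on the group difference at 12 months and says "our primary analyses are two subgroup comparisons: high-dose vs. low-dose and high-dose vs. placebo", each at 0.025, with no precondition. The end of II.C then names the mixed-model interaction as the primary analysis.

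No section gives a contrast between post-baseline visits, a slope estimand, or a rule for calling a decline progressive.

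**The concern.** The trial claims more than that a statin lowers respiration. It claims that the loss grows with duration. A test that reacts equally to a single early drop and to a continuing decline cannot support that by itself.

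The comparison that the trial is sized on, high dose against the other arms at month 12, also appears in V.A only as a follow-up to the interaction. Read literally, a real month-12 difference could go untested because the interaction was not significant.

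These are two different harms. Which one arises depends on whether month 0 is an outcome or only a covariate.

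**Working it through.** **The plan's own figure.** Two-sided two-sample t-test, d = 0.87, alpha 0.025, 80% power (II.C). The noncentral-t solution is n = 26.4, so 27 per group, with 81.0% power. Allowing 10% dropout, 27 / 0.90 = 30. The figure reproduces.

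**Inputs.** Effect 0.87 and alpha 0.025 come from II.C. Group sizes are 15 (completers, II.B), 20 (60 randomized / 3, II.B) and 27 (II.C). Assumed, because the documents do not say: complete data, equal correlation 0.5 between visits, low dose equal to placebo, and effects in SDs of change from baseline. With the SD of change equal to 1, the within-subject residual variance is 0.5.

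**Month 0 as an outcome; drop complete at month 1, then flat.** The high-dose profile over months 0, 1, 6, 12 is (0, −d, −d, −d), and the other arms are flat.
- Centring over four visits leaves a sum of squares of 3d²/4. Centring over three arms multiplies it by 2/3, giving d²/2.
- Noncentrality = n × (d²/2) / 0.5 = n·d², with d² = 0.7569. This is 11.35 / 15.14 / 20.44 for n = 15 / 20 / 27.
- On 6 and 9(n − 1) degrees of freedom, the interaction is significant in 68% / 83% / 94% of trials. Simulation gives 67% / 83% / 93%.
- If the test means a linear slope by group, simulation gives 37–38% / 48% / 62–63%.

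Nothing declines after month 1 in any of these trials.

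**Only months 1, 6 and 12 as outcomes; same effect.** The high-dose profile is (−d, −d, −d). Centred over visits it is zero, so the noncentrality is 0 and the interaction is significant only at its nominal 5% (4–5% simulated). That is correct behaviour for a test of duration dependence. As a precondition, it stops the month-12 comparison.

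**Month-12 power, high dose vs placebo, baseline-adjusted, 0.025.** At correlation 0.5 the SD at each visit is 1 and the residual SD is √(1 − 0.25) = 0.866, so the standardized effect is 0.87 / 0.866 = 1.005. The ranges for month 0 as an outcome cover the step and linear shapes. The last column is the step.

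| n per group | Unconditional | Conditional, month 0 an outcome | Conditional, months 1/6/12 only |
|---|---|---|---|
| 15 | about 65% | 47–49% | 3–5% |
| 20 | 79–82% | 66–71% | 3–5% |
| 27 | about 91% | 83–87% | 3–5% |

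At the pilot effect of 1.48 (88.5 / 59.9, II.C) with month 0 as an outcome, the condition costs almost nothing: 97–100% against 98–100%.

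**A direct duration contrast.** Take the high-vs-placebo difference at month 12 minus that at month 1. Under a linear decline to 0.87 at month 12, its true size is 0.87 × 11/12 = 0.7975 SD, with noncentrality 0.7975 × √(n/2) = 2.18 / 2.52 / 2.93. Power at two-sided 0.05 is 55–57% / 69–70% / 82%. Under the one-off drop it rejects at its nominal 5%.

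**The case against.** The case on the other side is substantial.

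- **The two harms need opposite readings.** With post-baseline outcomes only, the interaction does test duration dependence. With month 0 as an outcome, the 3–5% figure does not arise. A reader might infer that the plan fails on both counts at once, but no single reading of V.A gives that.
- **II.C calls the pairwise comparisons primary, with no condition.** A reader might infer from V.A that the month-12 comparison may never be made. Section II.C contradicts that, and V.A's time-point step can be read as extra localisation. What stands is that V.A and the end of II.C point the other way and the sections are not reconciled.
- **V.A does not say the interaction is a multi-degree-of-freedom test.** It speaks of a trend difference. A slope test reduces the false signal but does not remove it.
- **A plateau would be visible.** V.A plans least-squares means, and nothing there says that the location of the maximum decides whether decline is progressive. Significance together with a stepwise rise over months 1, 6 and 12 occurs in only about 12–16% of no-progression trials.
- **The pilot does not establish an early plateau.** Section I.C concludes that "skeletal muscle mitochondrial respiratory capacity and function declines rapidly with high dose atorvastatin therapy" and reports a progressive fall to about 50% by day 56. Constant absolute loss would reach zero at 56 / 0.50 = 112 days, so it cannot last 12 months, but a slowing decline could. Section II.C expects the fall to continue. The one-off drop is a case the analysis must distinguish, not a shape the documents predict.

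**Conclusion.** The point holds as a gap in V.A that should be fixed, with consequences that depend on the handling of month 0.

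If month 0 is an outcome, a significant interaction cannot by itself support a progressive or duration-dependent decline. The loss of month-12 power is moderate at d = 0.87 (about 16–18 points at 15 per group, 4–8 at 27) and close to nil at 1.48. If only months 1, 6 and 12 are outcomes, duration dependence is properly tested, but the precondition nearly always blocks the month-12 comparison for an early sustained effect.

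The percentages rest on complete data, equal correlation 0.5, low dose equal to placebo and the assumed effect shapes. The structural point does not. A reader might go further and infer that a plateau will be reported as progression. The documents support only a risk of that, because the visit means would show the profile.

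**What to change.** Change the wording of V.A, and align II.C with it:

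1. Test the two month-12 contrasts (high vs placebo, high vs low) from the mixed model at 0.025 each, as in II.C, without a prior interaction test.
2. Prespecify one duration contrast and its significance level, for example the high-vs-placebo difference at month 12 minus that at month 1. A post-baseline slope would also serve. Base any claim of progression on it.
3. Report the month 1, 6 and 12 differences with confidence intervals, in place of the search for the largest one.
4. State whether month 0 is an outcome or only a covariate. The contrasts in items 1 and 2 can be tested either way.

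No data collection changes. The cost is candour about power: the duration contrast has about 57% / 69% / 82% power (15 / 20 / 27 per group) even for a linear decline to 0.87 SD, so the progression claim may end up weaker than the month-12 claim.

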for 10% dropouts. The subject enrollment will be split equally between the two sites (15 participants/group per site). For this study, our primary analysis is to use mixed model to test the interaction between group and time, which is expected to be more powerful than the two-sample t-test because all repeated measurements will be considered in modeling, baseline patient characteristics can be controlled statistically, and participants with missing data can be included for analysis.

D. Subject Criteria

a. Inclusion criteria/Exclusion criteria:

- i. Inclusion Criteria
 - Ages 35–65 years
 - BMI between 25-43 kg•m²
 - >5% risk for a cardiovascular event in the next 10 years according to the 2013 American College of Cardiology/American Heart Association risk calculator and/or 2 out of 5 metabolic syndrome risk factors (Triglycerides ≥ 150 mg/dL; HDL ≤ 40 mg/dL; Glucose ≥ 100mg/dL; Waist Circumference ≥ 102cm for males, 88cm for females; Blood pressure: ≥ 130mmHg systolic and/or 85mmHg diastolic or being treated for hypertension) and/or LDL-Cholesterol >120 mg/dl.
 - Stable doses of medications for 90 days
 - Willing to stop all NSAIDs and aspirin for 7 days prior to muscle biopsy

[figure not shown]
ii. Exclusion Criteria

- Smoking
- Previous use of statins
- Use of other medications or supplements that affect lipid profiles or body weight in the last 6 months
 - o e.g., fibric acids, bile acid sequestrants, nicotinic acids, fish oil
- Diagnosis of chronic diseases including CVD, other metabolic diseases (e.g., thyroid), current diagnosis and active treatment of cancer, HIV, or acquired immunodeficiency syndrome.
- Diagnosis of type 1 or type 2 diabetes at the time of screening (fasting blood glucose >126mg/dL). If evidence of type 2 diabetes outcome measures is detected during the course of the study (fasting glucose > 126 mg/dl or HbA1c > 6.5%) we will notify the participant to contact their physician.
- History of abnormal bleeding problems
- Currently taking (within the last 10 days) anti-platelet medication (Plavix), Warfarin, and other anti-coagulants (eliquis, pradaxa, and xarelto) medications.
- >2 fold upper normal limit (UNL) for ALT or creatinine
- Women who are pregnant or breastfeeding
- Individuals with polymorphism (SLCO1B1) known to be associated with susceptibility for statin induced myopathies (tested at screening)
- Currently enrolled in another research study

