 - c. Providing on-going information to the study sponsor and the IRB: PI, Study Coordinator
 - d. Maintaining participant's research records: PI, Study Coordinator
 - e. Completing physical examination: PI, CTSU Nurse
 - f. Taking vital signs, height, weight: CTSU Nurses
 - g. Drawing / collecting laboratory specimens: CTSU Nurses
 - Performing / conducting tests, procedures, interventions, questionnaires: PI,
 Study Coordinator
 - i. Completing study data forms: Study Coordinator
 - j. Managing study database: PI

K. Assessment of Subject Safety and Development of a Data and Safety Monitoring Plan

- **a. Key personnel:** [name], [name], [name], [name], study physician at KUMC and [name], study physician at ECU.
- b. Plan for safety monitoring and review: [name] will serve as the Chair of the Data Safety Monitoring Board and will convene every 6 months with the other members, Drs. [name] and [name] to make decisions on safety of the participants. Enrollment data will also be reviewed twice a year by the DSMB. In addition, data will be reviewed on a yearly basis with the biostatistician, [name] to determine if the studies should be shortened do to either no measured effect or due to effects that are greater than what power calculations indicated. If problems occur with participants, blinded study staff will alert [name]. [name] will have access to dose and type of statin and will consult the study physicians/cardiologist to make a decision on whether the subject should be removed from the study for safety concerns. The PI and other key personnel will be examining research data on a subject to subject basis to ensure it is accurate and to address any potential problems that may arise with the protocols. In addition, Drs. [name] and [name] will discuss data at least once per month through in person meetings or by phone to ensure that data collection is occurring in a consistent manner at both locations.
- **c. Plan for adverse event reporting:** Adverse events will be defined as any untoward medical occurrence in study participants or others immediately involved in the

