- **C. Tissue Banking Considerations:** Following completion of the current project, remaining blood and tissue samples will remain in locked freezer indefinitely. Samples will only be used by investigators of the current project, both KUMC and ECU, when a new biomarkers or techniques of interest emerge.
- **D. Procedures to protect subject confidentiality**: Risks to confidentiality are reduced by assigning all participants to a data code. Folders are stored in locked file cabinets, and only the PI and study coordinator have access to the locked files. Individual names or initials are not used in any discussions or publications of the data.
- **E. Quality Assurance / Monitoring:** Data will be reviewed twice a year by the Board Chair. In addition, data will be reviewed on a yearly basis with the biostatistician, [name] to determine if the studies should be shortened do to either no measured effect or due to effects that are greater than what power calculations indicated. The PI and other key

personnel will be examining research data on a subject to subject basis to ensure it is accurate and to address any potential problems that may arise with the protocols. In addition, Drs. [name] and [name] will discuss data at least once per month through in person meetings or by phone to ensure that data collection is occurring in a consistent manner at both locations.

V. Data Analysis and Reporting

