- B. Expected Outcomes: Atorvastatin therapy will induce a progressive decline in skeletal muscle mitochondrial respiratory capacity that will be evident both in vivo (i.e., whole muscle NIRS) and in situ (i.e., respirometry in permeabilized fiber bundles). Based on the rationale outlined above and our preliminary data, we anticipate mitochondrial function will decline in a dose x time-dependent manner, occurring sooner in the high- verses low- dose treatment group. We further predict that the effect will be inversely related to the initial mitochondrial respiratory capacity of the skeletal muscle. Loss of mitochondrial functional capacity/content is predicted to, in turn, compromise the ability to maintain cellular redox homeostasis. Based on our previous findings (61), a shift to a more oxidized cellular redox state in skeletal muscle is expected to negatively impact insulin action. We also anticipate mitochondrial Ca2+ retention capacity will be reduced by statin therapy, providing a potential mechanism for the loss of mitochondrial content over time. If this occurs, follow up measures of genes and proteins controlling Ca2+ retention capacity (mitochondrial calcium uniporter and antiporter), and apoptosis and mitophagy (Bcl-2 (anti-apoptotic)/Bax (proapoptotic) will be performed to determine if these pathways are altered by low or high dose statins. Consistent with the reductions in mitochondrial function, we expect whole body insulin sensitivity and cardiorespiratory fitness (VO2 max) to also be reduced in a dose and time dependent manner (i.e., downstream of declines in mitochondrial function) in response to statin therapy. Of particular interest will be to determine whether reductions in mitochondrial respiratory capacity are associated with lower pain threshold and higher CK levels at rest and/or in response to exercise testing, and whether such changes are associated with compromised indices of cardiovascular function (increased heart rate and/or

reduced stroke volume), potentially occurring secondary to mitochondrial dysfunction in skeletal muscle or in another cell type like endothelial cells. Most of the data, since it is collected in real-time, will be analyzed as the study progresses allowing us to stop the study early should statistical differences in the primary outcome measures be detected prior to completion.

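### The protocol allows early stopping on unadjusted significance in the primary outcome, so the claimed overall 5% type I error is not protected if that permission is used

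*Combined protocol and SAP*

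**What the plan says.** - **Error control (II.C).** The two primary comparisons, high dose against low dose and high dose against placebo, are each tested "at 0.025 level to maintain the overall type I error rate at 0.05 level for the two group comparisons". The sizing statement is: "With 27 participants in each group, a two-sided two sample t-test has 80% power", at an effect size of 0.87.
- **Planned test (II.C and V.A).** II.C says "our primary analysis is to use mixed model to test the interaction between group and time". V.A repeats this: "Two-way interaction between treatment and time will be added in the model for testing if the outcome changes differently between groups over time". V.A does not mention interim use of the test.
- **Stopping on significance (V.B).** The last sentence of Expected Outcomes plans analysis of most data during the study, "allowing us to stop the study early should statistical differences in the primary outcome measures be detected prior to completion".
- **A second criterion (II.K.b and IV.E).** Under IV.E, "data will be reviewed on a yearly basis with the biostatistician", to decide whether the studies "should be shortened do to either no measured effect or due to effects that are greater than what power calculations indicated". II.K.b has the same wording.
- **DSMB (II.K.b).** The chair "will convene every 6 months with the other members". That text concerns safety and enrolment and sets no outcome boundary.

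No section states how many outcome analyses there will be, what threshold applies at each, how the final test is adjusted, or what counts as no measured effect.

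**The concern.** Splitting 0.05 into two halves pays for two comparisons made once. Each further test of accruing data that can end the trial with a positive claim is another chance of a false positive, and nothing in II.C pays for it. Treatment lasts 12 months, so a yearly review counted from the start of enrolment falls before the last 12-month visit unless everyone enrols at once.

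The two criteria also differ. V.B responds to statistical significance; II.K.b and IV.E respond to the size of the effect or its absence. A reader cannot tell which one governs. If the trial stopped early with a positive result, the protocol would give no basis for a valid p-value.

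**Working it through.** **1. The plan's own figures.** Inputs from II.C: d = 0.87, two-sided 0.025 per comparison, power 80%, dropout 10%.

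- Normal approximation: n = 2(z₀.₉₈₇₅ + z₀.₈₀)²/d² = 2(2.241 + 0.842)²/0.757 = 25.1, so 26 per group.
- The noncentral t gives power 79.3% at 26 and 81.0% at 27, so 27 per group is right.
- 27/0.90 = 30 recruited per group, as stated.
- Error for one analysis: 0.025 + 0.025 = 0.05 as an upper bound. Because the comparisons share the high-dose arm, the simulated value is about 4.7%. The II.C claim holds for one analysis.

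**2. Repeated unadjusted analyses.** Assumed, because the documents do not say: number and timing of analyses (final counted), 0.025 per comparison each time, and JO₂ as the only tested variable. Method: three normal groups with no effect, two-sample t-tests at equally spaced cumulative n, 200,000 simulated trials per setting. Both sizes are shown because II.B aims for 15 completers per group and II.C is powered on 27.

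| Analyses | 15 per group | 27 per group |
|---|---|---|
| 1 | 4.7% | 4.7% |
| 2 | 7.9% | 7.9% |
| 3 | 10.7% | 10.5% |
| 4 | 12.6% | 12.3% |
| 5 | 14.5% | 14.3% |

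Spacing matters: three analyses bunched late give about 8.5-9.6%.

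**3. The planned type of test at yearly reviews.** Assumed: uniform accrual, reviews at months 12, 24 and so on, a final analysis after the last 12-month visit, visits at 0, 1, 6 and 12 months, within-person correlation 0.5 (0.3 or 0.7 moves results by at most 0.3 points), known covariance and no dropout. Cells are 15 / 27 per group.

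| Accrual (analyses) | Group-by-time, all visits | 12-month difference only |
|---|---|---|
| 1 year (2) | 7.6% / 7.5% | 4.6% / 4.7% |
| 2 years (3) | 10.5% / 10.5% | 7.4% / 7.5% |
| 3 years (4) | 12.8% / 12.9% | 9.8% / 9.7% |
| 4 years (5) | 14.7% / 14.7% | 11.4% / 11.5% |

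The right-hand column is lower because the first yearly review has no 12-month data.

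**4. The effect-size criterion alone.** Read as: stop if the observed d in either comparison exceeds a threshold, then test at 0.025. Three equally spaced analyses. II.C offers two candidate thresholds: 0.87, the powered effect, and 1.48, the pilot effect for JO₂.

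| Threshold | Direction | 15 per group | 27 per group |
|---|---|---|---|
| 0.87 | either | 6.3% | 7.9% |
| 0.87 | high dose worse only | 5.5% | 6.3% |
| 1.48 | either | 8.2% | 5.5% |
| 1.48 | high dose worse only | 6.4% | 5.0% |

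**5. What a boundary would cost.** O'Brien-Fleming, three equally spaced analyses, two-sided 0.025 per comparison: the final critical value is 2.27, and analysis k uses 2.27√(3/k), that is 3.93, 2.78 and 2.27. The nominal p-values are about 0.0001, 0.005 and 0.023. Overall error across both comparisons is about 4.7%. Power per comparison at d = 0.87 goes from 80.8% to 80.4% at 27 per group and from 51.3% to 50.5% at 15.

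**The case against.** **The size is assumed.** This is correct: every inflated figure depends on a number and timing of analyses that the protocol does not give. It limits the magnitude but not the defect, since the missing number is part of what is wrong.

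**There may be no inflation.** II.C sizes the trial on the difference at 12 months. With 1-year accrual and yearly reviews restricted to that difference, error stays at 4.6-4.7%. A reader might infer that the 5% fails under any use of either criterion; the documents do not support that. Against this, II.C and V.A name the group-by-time interaction as the test, and V.B is not limited to 12-month data.

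**The text is permissive narrative.** The V.B sentence sits under Expected Outcomes. It still states when the study may stop, and II.K.b and IV.E separately allow shortening on outcome data.

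**A stop for no effect would lower the error.** It would if it were binding and defined, and it is neither. A reader might also infer that this clause would end most trials that have a real effect. The documents give no rule from which to calculate that. Reading it as a non-significant result cannot work as a binding rule beside the significance stop, because every trial would then end at its first analysis.

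**The unblinding in IV.A.** A reader might take the 1-year unblinding of the PIs and the biostatistician as a further stopping rule. IV.A contains none. How it fits with the blinding statement in II.E.a.xiv is a separate point to reconcile.

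**Conclusion.** The concern stands in conditional form. The protocol claims 5% overall error, its split protects that only for one analysis, and its stopping permissions carry no adjustment. If they are used, the size depends on how:

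- significance at each analysis, equally spaced: about 8% (2 analyses), 10-11% (3) and 14-15% (5), with similar values for the group-by-time test at yearly reviews;
- yearly reviews of the 12-month difference only: from about 4.7% (1-year accrual, no inflation) to about 11.5% (4 years);
- stopping only on an effect above the powered one, 3 analyses: about 5-8%, depending on direction, group size and threshold.

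Confidence is high that a rule is missing and lower for any single figure. The t-test results are illustrative because the planned test is a mixed model; step 3 addresses this for type I error but not for power. All figures treat JO₂ as the only tested variable. V.B speaks of primary outcome measures in the plural, and testing several would add to the error.

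**What to change.** Choose one of two routes before any further outcome review.

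1. **Single analysis.** Remove the significance-based early stopping from V.B, remove the outcome-based shortening from II.K.b and IV.E, and test maximal ADP-stimulated JO₂ once after the last 12-month visit. This costs wording only, and the 0.025 per comparison then does what II.C claims.
2. **One prespecified rule.** Reconcile V.B, II.K.b and IV.E into a single outcome-monitoring rule reviewed through the DSMB. State the number and timing of analyses, the tested variable (maximal ADP-stimulated JO₂) and the test. Set an alpha-spending boundary for each comparison, for example of O'Brien-Fleming type, and replace the no-measured-effect wording with a defined, non-binding futility criterion. With three equally spaced analyses the final level is about 0.023 instead of 0.025, and power falls by under one point in t-test simulations. Recompute the boundary for the actual information times and the mixed-model test, because yearly reviews will not be equally spaced in information.

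Under either route, add the chosen rule to V.A and leave the DSMB safety review unchanged.
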